#### Figure 2. Overall study design

D=Day; EoS=end of study; M=month;

\* Study site visit; \*\*Investigator contact.

The design of this study (double-blind and placebo-controlled) is the unique opportunity to estimate prevalence of extravascular dermal *T.b. gambiense* in a large population of seropositive individuals who are non-confirmed parasitologically and to compare the effectiveness of new methods to monitor the presence of dermal trypanosomes in seropositive unconfirmed individuals. Therefore, to allow this comparison, molecular and immuno-histochemical tests will be performed at baseline and at the month 4 (EoS) visit for all subjects, who will be willing to participate in the TrypSkin sub-study.

## 4. Selection of subjects

The following eligibility criteria are designed to select subjects for whom the protocol treatment is considered appropriate. All relevant medical and non-medical conditions should be taken into consideration when deciding whether this protocol is suitable for a particular subject. Eligibility criteria may not be waived by the investigator. Any questions regarding a subject's eligibility should be discussed with DNDi medically responsible person prior to the subject's enrolment.

#### 4.1. Inclusion criteria

Subjects must meet all the following inclusion criteria to be eligible for enrolment into the study and sub-study:

- Signed the informed consent form
- Male or female
- 15 years of age or older
- CATT test or HAT sero-K-set RDT positive
- Parasitology negative (in blood and/or lymph (if lymphadenopathy is present)
- Karnofsky Performance Status above 70
- Able to ingest oral tablets
- Known address and/or contact details provided
- Must be able to comply with the schedule of follow-up visits and other requirements of the study
- Agreement to be hospitalised upon enrolment for at least 5 days (in order to receive in-ward post-treatment observational follow-up through the first 5 days after treatment)
- Agreement to not take part in any other clinical trials during the participation in this

#### study

- For women of childbearing potential:
  - Must agree to have protected sexual relations to avoid becoming pregnant from enrolment up to 3 months after dosing (contraceptive protection will be advised and offered at no cost).
  - Negative urine pregnancy tests (before dosing at site level)

## 4.2. Exclusion criteria

The presence of any of the following criteria will exclude a subject from study enrolment:

- Individuals parasitologically confirmed in blood and/or lymph
- Previously treated for g-HAT
- Severe malnutrition, defined as body mass index (BMI) <16 kg/m^2
- Pregnant or breast-feeding women
- For women of childbearing potential:
  - Urine pregnancy test positive
  - Do not accept contraceptive protection (i.e. condom or sexual abstinence) from enrolment up to 3 months after dosing
- Clinically significant medical condition and/or abnormal laboratory results that could, in the opinion of the Investigator, jeopardise the subject's safety or participation in the study

#### Additional exclusion criteria for TrypSkin sub-study:

- Rejection to participate in the sub-study in the signed ICF
- Known diabetes
- Known haemophilia

#### 5. Schedule of events

The schedule of events is presented in Table 1.

Protocol Version/Date: Version 3.0 of 13 June 2023

#### Table 1. Schedule of Events

	Hospitalisation					Follow-up				
	Screening (before dosing)	Dosing	ng Post dosing period					Site visit		
	D-2 to D1H0	D1H0	D1	D2	D3	D4	D5	M1	M4 (EoS)	
Informed consent (Main study + TrypSkin sub-study  )	Х									
Serological test (CATT or HAT sero-K-set RDT)	Х								X 	
Parasitological test(s) 	Х							Х	Х	
Pregnancy test 	Х							Х	Х	
Demographics	Х									
Medical History	Х									
Concomitant medications record	Х	Х	Х	Х	Х	Х	Х	Х	X	
Karnofsky index	Х							Х	Х	
Physical and clinical examination (including HAT signs and symptoms & vital signs)	Х						х	Х	x	
Dermatological examination	Х							Х	Х	
Blood pressure	Х		X 				Х	Х	Х	
Haematology /Biochemistry	Х						Х	Х	Х	
Inclusion/Exclusion review	Х									
Randomisation/Treatment		Х								
ECG 	Х						Х			
Trypanolysis test 	Х									
Blood PK (on DBS)							Х	Х		
Collection of AEs	Х	Х	Х	х	Х	Х	Х	Х	Х	

TrvpSkin sub-study procedures

Blood sampling for molecular biology	Х				Х
2 mm-skin-punch biopsies for IHC and molecular biology	Х				Х

AE=adverse event; CATT=card agglutination test for trypanosomiasis; D=day; DBS=Dry Blood Spot; ECG=electrocardiogram; EoS=End of Study; H= Hour; IHC=immunohistochemistry; M=month; PK=Pharmacokinetics; RDT=rapid diagnostic test.

1. For sites participating in the TrypSkin sub-study only

2. At M4, same serological test than baseline to be repeated

3. mAECT or mAECT-BC and lymph node puncture if suspicious enlarged cervical lymph nodes are detected.

4. For women of childbearing potential only.5. At D1, blood pressure will be taken 1 hour before dosing, at D1H4 and at D1H9

6. ECG triplicate recording at pre-dose on D1 and D5 according to acceptable time window described in section 8.3.6.

7. Not for inclusion but as a reference test for follow-up.

## 6. Enrolment procedures

The study is planned to be conducted in study sites located in regions of the DRC and Guinea, where HAT disease is endemic, and personnel is trained and has experience in HAT clinical trials and in treating patients with the disease.

In order to select a more uniform study population across sites and countries in terms of HAT suspicion, only subjects referred by mobile teams (i.e. active case-finding) will be included in the study. For more details about algorithm for subject's identification and screening process, please refer to Appendix 2.

#### 6.1. Identification at the village level (under the responsibility of NSSCP)

During the course of their usual active case-finding activities, the mobile teams of the NSSCPs of DRC and Guinea identify seropositive individuals (by positive result to one of the serological tests: CATT or HAT Sero-K-Set RDT) that are not parasitologically confirmed at the diagnostic point (village). Those individuals will be notified about the study. Those interested in participating in the study and that have not been previously treated for g-HAT, are not pregnant (a urine pregnancy test could be performed at the discretion of the mobile teams to avoid unnecessary displacements to clinical sites), or breastfeeding, will be invited to attend a visit at the clinical site. Note that all people seropositive (by CATT or HAT Sero-K-Set RDT) and parasitologically confirmed will be taken under NSSCP responsibility for appropriate treatment. Those presenting any of the serological test positive and presenting a pregnancy test positive or breast-feeding or pregnant women will be regularly followed-up by the NSSCP.

#### 6.2. Screening and enrolment procedures at clinical site level

- (i) The individuals referred to clinical sites by the NSSCP will be invited to participate in the safety main study and eventually in the TrypSkin sub-study by signing the ICF. The subject can decide to participate or not in the TrypSkin sub-study independently of his/her participation in the main study. His/her declining to participate in the substudy will not impact his/her participation in the main study.
- (ii) After the ICF signature process, all inclusion/exclusion criteria will be checked. If any of the requirements for inclusion are not confirmed, the participants will be classified as a screen failure subject and will be referred to the NSSCP for appropriated management.
- (iii) For those who agree to participate in the safety main study, dry blood spots (DBS) will be obtained for a Trypanolysis (TL) test. The TL test is only performed in reference laboratories and receipt of test results could be delayed for several weeks. Therefore, TL result will not be a criterion for inclusion but will be used to classify subjects at the end of the study for addition in the final data analysis. If the TL test is positive, there is a higher probability of the subject being a true case. Upon exiting the study and as soon as TL results are available, it will be ensured that TL positive individuals are referred by the clinical sites to the NSSCP for appropriate surveillance. Upon study unblinding, the treatment arm will be communicated to the NSSCP to ensure the TL positive individuals having received placebo have the appropriate parasitology follow-up assessment. Those who are lost to follow-up will be reported to NSSCP.
- (iv) For subjects that will be enrolled in the TrypSkin sub-study: five additional DBS, a 3 mL blood sample and two skin punch biopsies will be obtained for molecular analyses.
- (v) Enrolled subjects will be randomised (double blind, unbalanced 3:1 randomisation) into the acoziborole or placebo arm.

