#### 7.7.2. Unblinding Measures

If unblinding is required in the interest of the safety of a subject, the site Investigator will discuss the matter with the Sponsor/Study Principal Investigator and/or the National Coordinating Investigator before scratching the individual code-break card for that subject, unless in a medical emergency, when the site Investigator or delegate may open the individual code-break card for that subject without prior consultation with the Sponsor/Study Principal Investigator and/or the National Coordinating Investigator. The site Investigator or delegate will notify the Sponsor as soon as possible, i.e. within 24 hours if possible, that the randomisation code has been broken for the subject with the justification and the participant number.

If the randomisation code is broken by the Investigator, the reason will be fully documented in the appropriate document provided with the individual code-break card.

The DSMB may exceptionally request unblinding of certain subject(s) (e.g. in case of a major safety concern), but only if absolutely necessary, and always in accordance with the DSMB Charter, therefore preventing unblinding the sponsor personnel.

Treatment allocation of all trial participants will be unblinded after the database lock.

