#### 7.9. Medical cares after trial ended

At the end of the study, after unblinding, the NSSCP will be informed of the subjects' study status (TL results at baseline, treatment arm and parasitology results at EoS) for appropriate follow-up according to NSSCP policy as follows:

- a) those included in the study and treated with acoziborole and TL positive
- b) those included in the study and treated with acoziborole and TL negative
- c) those included in the study treated with placebo and TL positive
- d) those included in the study treated with placebo and TL negative.

Since the inclusion time-period is expected to last for 12 months and the follow-up is planned for 4 months after treatment, the first study subjects included in the study may have to wait 1 year before knowing whether he/she has been treated with acoziborole or placebo. Therefore, while waiting for the end of the study, and the unblinding, subjects who conclude their 4 months of follow-up study visit (and especially those with TL positive results) will be referred to the NSSCP for the continuation of the NSSCP's standard follow-up management.

For follow-up of women who become pregnant during the study and their newborn babies after the end of their trial participation, please refer to Section 8.5.9.

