3.4.4. Determining actual treatment received

Treatment misallocation was identified during the study through PK analysis where samples from a few participants expected to be randomized in the acoziborole arm showed no concentration of acoziborole. Therefore, it was decided to analyze 1 timepoint of PK samples for all participants (i.e. D5 sample and if D5 sample is not available then M1 timepoint) for detection/non-detection of acoziborole in blood purposes. Since this is primarily a safety study, it is conservative to consider participants to have taken active treatment as long as there is detection of any amount of acoziborole in blood; thus, any safety events in those patients would be attributed to acoziborole given its long half-life. Since study drug is only taken once, participants with no acoziborole detected by PK after that dose will be assumed to have taken placebo. The PK concentration data will then be used to determine the actual treatment received which will be merged with other Study Data Tabulation Model (SDTM) datasets at unblinding.

4. Trial Population

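### After unblinding, the control programme should be told the treatment each participant actually received, beside the randomised arm

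*Protocol*

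**What the plan says.** The protocol describes in four places what the NSSCP is told once the study is unblinded.

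- Protocol 6.2(iii): "Upon study unblinding, the treatment arm will be communicated to the NSSCP to ensure the TL positive individuals having received placebo" get a parasitology follow-up assessment.
- Protocol 7.9: the programme is told each subject's status, given as "TL results at baseline, treatment arm and parasitology results at EoS". Four groups follow, worded by what people were treated with, for example "those included in the study treated with placebo and TL positive".
- Protocol 15.3: the same list as 7.9 with serology added, again naming the treatment arm.
- Protocol 8.3.3: the text runs almost parallel to 6.2(iii) and has the same purpose, but the item communicated is the treatment that participants received.

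Protocol 15.4 also mentions sharing subject data after unblinding, without naming either variable.

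SAP 3.4.4 records that treatment misallocation was found during the study: "samples from a few participants expected to be randomized in the acoziborole arm showed no concentration of acoziborole". One PK timepoint (Day 5, or Month 1 if Day 5 is missing) is therefore analysed for everyone. The rule is that "participants with no acoziborole detected by PK after that dose will be assumed to have taken placebo". In the other direction, "it is conservative to consider participants to have taken active treatment as long as there is detection of any amount of acoziborole in blood". The PK data are "used to determine the actual treatment received which will be merged with other Study Data Tabulation Model (SDTM) datasets at unblinding".

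**The concern.** The hand-over has a clinical purpose. Protocol 6.2(iii) says a TL-positive person is more likely to be a true case, and the programme needs to know which of these people had no active drug so that their parasitology is followed up. That depends on what was swallowed. Three of the four passages nevertheless name the arm, and the SAP shows that arm and treatment received differ for some participants.

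The documented mismatch also runs in the direction that matters. If the randomised arm is sent, a TL-positive participant assigned to acoziborole, with none detected in blood, would appear on the list as an acoziborole recipient. That person could miss the follow-up meant for placebo recipients.

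**Working it through.** No sample size, power or error rate is involved. The check is a comparison of passages.

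**Step 1. Which variable does each passage name?**

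| Protocol section | Variable named | Cue to the intended meaning |
|---|---|---|
| 6.2(iii) | Treatment arm | Purpose clause refers to people who received placebo |
| 7.9 | Treatment arm | Groups (a) to (d) are worded by what people were treated with |
| 15.3 | Treatment arm | None |
| 8.3.3 | Treatment received | Same purpose clause as 6.2(iii) |

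The count is three to one. Read for purpose, 6.2(iii), 7.9 and 8.3.3 all point to treatment received. Read literally, the arm is the randomised arm: 6.2(v) uses the word that way, and 7.7.2 says "Treatment allocation of all trial participants will be unblinded after the database lock".

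**Step 2. Are the two variables different in this trial?** Yes. SAP 3.4.1 reports the ITT and mITT sets as randomised. SAP 3.4.2 analyses the safety set by actual treatment, determined by PK detection. SAP 3.4.4 says some participants are discordant.

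**Step 3. Is non-detection credible evidence of no active drug?** SAP 1.1 gives a Tmax of about 72 h and a half-life of about 400 h. The Day 5 sample is taken at 96 h, close to the peak. The fallback Month 1 sample is at 30 × 24 = 720 h, which is (720 − 72)/400 = 1.62 half-lives after Tmax. Under simple first-order decay, 0.5^1.62 = 0.33 of the peak would remain. The assay limit is not given, but an undetectable result after a full dose would be surprising at either time.

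**Step 4. What would each variable report?**

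| Randomised arm | PK result | Listed if arm is sent | Listed if SAP 3.4.4 treatment is sent |
|---|---|---|---|
| Acoziborole | Detected | Acoziborole | Acoziborole |
| Acoziborole | Not detected | Acoziborole | Placebo |
| Placebo | Not detected | Placebo | Placebo |
| Placebo | Detected, any amount | Placebo | Acoziborole |
| Either | No sample | As randomised | Undetermined |

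The second row is the case that the SAP documents, and sending the arm gets it wrong. Substituting the SAP variable corrects that row but opens two gaps. In the fourth row, a placebo-arm person with a trace result moves into the treated group. The any-amount rule is conservative for attributing safety events, but works the opposite way for deciding who needs follow-up. In the fifth row there is no determined treatment at all. The substitution therefore needs a rule for both rows.

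**Step 5. Can the number affected be estimated?** No. The SAP's few participants were found before the decision to test everyone; Protocol 8.3.4 had planned PK analysis only for the first 192 subjects with a valid ECG and a Day 5 sample. The documents give no TL-positivity rate and do not say which variable will be put in the listing. With all three inputs missing, any probability would only restate its own assumptions.

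**The case against.** The strongest reply is that the text, read in context, already means treatment received. The purpose clause in 6.2(iii), the groups in 7.9 and the plain wording of 8.3.3 all say so, and only 15.3 lacks a cue. Section 6.2(v) describes randomisation and 7.7.2 says when the code is broken; neither defines the hand-over variable. The protocol itself does not mention misallocation, and without it the two terms coincide. This stands as evidence of intent, and it reduces the point to one of wording. It does not remove the point, because nothing links the arm named in three sections to the PK-determined treatment in SAP 3.4.4, and whoever builds the listing could follow the literal words.

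The second reply is that little harm would follow. This also largely stands. All TL-positive people are referred for surveillance whatever their arm (6.2(iii), 8.3.3, 15.3). Parasitology is repeated at Months 1 and 4. National policy already advises regular parasitology for unconfirmed seropositive people (1.6). Follow-up is left to NSSCP policy, and the documents do not say how it differs for acoziborole recipients.

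A reader might infer three stronger things that the documents do not support:

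- That participants will be misreported. No passage says that the randomised arm will be sent in preference to treatment received.
- That untreated TL-positive people will be left without care. The general referral applies to them too.
- That the safety results are affected. SAP 3.4.2 and 5.1 already analyse by actual treatment, with a sensitivity analysis excluding misallocated subjects.

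**Conclusion.** The inconsistency is real and minor; correcting it is a cheap improvement. The protocol intends the NSSCP to know who received placebo, three of its four passages name a variable that can get this wrong, and the SAP documents participants for whom it would. The size is unknown. Nobody is misreported if treatment received is sent, or if no discordant participant is TL-positive; the documents cannot show that the count is zero, nor that it is small.

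The conclusion rests on two things: that *treatment arm*, taken literally, is the randomised arm, and that the SAP rule for non-detection correctly identifies people without active drug. The possible harm is confined to the extra parasitology follow-up aimed at placebo recipients.

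**What to change.** In Protocol 6.2(iii), 7.9 and 15.3, state that the NSSCP receives the actual treatment received, as determined under SAP 3.4.4, listed beside the randomised arm. If an amendment is not warranted, put the same statement in the specification of the hand-over listing.

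Add one handling rule. Any TL-positive subject who is discordant in either direction, or who has no PK result, is flagged and handled as a placebo recipient for parasitology follow-up. Only those randomised to acoziborole with drug detected then count as treated for this purpose. This covers the documented case, the trace result in a placebo-arm subject, and the missing sample.

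The cost is wording in three sections, or one specification note, plus two columns in the listing (treatment received and a flag). No new assay is needed, because SAP 3.4.4 already orders one PK timepoint for everyone and merges the result at unblinding. An amendment may require ethics committee submission under Protocol 13. A few subjects may be followed up who did not need it.

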## 7. Study treatments

#### 7.1. DNDi study treatment

The IP is acoziborole 320 mg or matching placebo tablets.

The IP will be provided by DNDi, [name]. For more details about acoziborole, please refer to the last version of the Investigator Brochure.

#### 7.2. Comparator study treatment

No active comparative treatment will be used in this study.

#### 7.3. Doses and treatment regimens

Acoziborole or matching placebo will be administered to subjects by the oral route in the fasting state according to the following dosing regimen:

• 960 mg (three tablets) in a single intake on Day 1 of the study

#### 7.4. Study treatments labelling, packaging

The IP will be packaged in aluminium-aluminium blister packs. Each pack will contain the number of tablets required for one administration (three tablets) and will be packaged in an individual treatment kit of each subject.

The labelling on the treatment kit will display the following information:

- Name of the Sponsor\* and name and contact details of the Coordinating or Principal Investigator
- Study number\*
- Name\* and dose strength of the IP
- Dosage form\*, route of administration\*, and number of dose units
- Instructions for use
- The statements "for clinical study use only" and "keep out of the reach of children"
- Batch number\* and number of treatment kit\*
- Expiry date and storage conditions

The information items marked with an asterisk (\*) will also be displayed on the immediate packaging of the IP.

Information on acoziborole will be provided in the Investigator's Brochure, attached to the protocol submitted to the Competent Authorities.

#### 7.5. Accountability

The study-specific forms must be used for accountability of the IP. Appropriate records concerning receipt, use, return, loss, or other disposition of the IP must be maintained by the Investigators at the study centres or by their delegates, under the supervision of the Principal Investigator. In addition, the study monitors must check accountability of the IP during their on-site monitoring visits.

In the study centres, the IP must be stored in a locked room or a locked cabinet with access limited to the person in charge of the pharmacy or authorised study personnel.

The IP must not be used for purposes other than the present protocol. The Investigator and the study personnel may not, under any circumstances, provide other investigators or healthcare services with the IP attributed to their study centre or allow IP to be used other than as described in this protocol without prior written approval from DNDi.

